4 OBJECTIVES OF THE STUDY

Primary objective:

• Evaluate the feasibility of HIV self-testing (HIVST) delivery by a private pharmacy network among men who have sex with men (MSM) and transgender women (TGW) recruited through a classic and digital Respondent Driven Sampling method to improve HIV testing in Phnom Penh, Cambodia

Secondary objectives:

- Evaluate the acceptability and appropriateness of the strategy
- Identify barriers and facilitators
- Estimate the linkage to confirmatory testing for those with a reactive test and linkage to HIV care and ART for those with a positive confirmatory HIV test
- Estimate linkage to pre-exposure prophylaxis (PrEP) services for negative participants
- Estimate the characteristics of participants and compare to those reported in Integrated Biological and Behavioral Survey (IBBS 2019) for MSM and TGW in Cambodia
- Evaluate the adherence of participants to a 6-monthly repeated HIV testing

5 METHODOLOGY

Study design

An interventional pilot study using a mixed qualitative and quantitative approach will be carried out in order to evaluate the feasibility, acceptability and appropriateness of the strategy and to identify barriers and facilitators.

The participant recruitment method will be designed as a Respondent Driven Sampling (RDS) by recruiting initial seeds both at hotspots and on social networks.

After 6 months, a qualitative assessment by focus groups discussion (FGD) will be conducted among MSM, TGW and pharmacists to evaluate feasibility, acceptability and appropriateness of the intervention and to identify barriers and facilitators.

Each participant will be followed during 18 months and encouraged to perform a 6-monthly HIV testing during this period.

Study overview

The intervention will be designed as a RDS by recruiting initial seeds both at hotspots and on social networks. 15 initial seeds will be recruited. Seeds will come to the study site for checking inclusion criteria and receiving information on self-testing, benefits of their participation and recruiting other participants in their networks along with the important details about the study. Once consent to the study, the seed is provided with two types of coupons for HIVST kit at partner pharmacy: 5 electronic coupons (e-coupons) consisting of a pictured unique anonymous QR code and identifier and address of partner pharmacies; 5 paper coupons consisting of a printed unique anonymous QR code, identifier and address of partner pharmacies. The seeds will then distribute

Version 1.1 du 18/04/2022

electronic and paper coupons to their networks physically and via social media, messaging and calling applications such as Twitter, Whatapp and Telegram (e-coupons).

Each recruited participant will bring the coupon to be scanned at partner pharmacies to receive direct and free access to one HIVST kit. Partner pharmacies with a proper dedicated room/space securing privacy and secrecy in Phnom Penh are the study sites. There, trained community worker/research team who get notified by partner at each visit of participant will do the study visit including information/consent, e-CRF filling and give a link of an external website to send the HIV test results and receive information or advices.

These recruited individuals will be considered as wave 1 of recruitment and will each receive 10 additional coupons to recruit the members of their networks. The next round of individuals recruited and enrolled will be considered as wave 2, and so on. The number of 10 coupons was selected to avoid a bias risk related to participation incentives.

To facilitate the return of HIVST kit results, participant will upload the picture of results labeled with their identifier directly using the link of the external website that they received from community worker/research team during their visits at pharmacy. In case of any question, they could reach community worker/research team by hotline number. According to the results, the participants will be proposed with a support for linkage to confirmatory test or to PrEP services. Each non-reactive participant will be provided another new coupon (paper or electronic format upon their preference) with a reminder to perform a 6-monthly HIV testing during 18 months. They will not be granted any token or incentives if they fail to return the result of HIVST kit taken at pharmacies. These incentives are also added upon the number of recruited members of their networks using common money transfer and payment services in Cambodia such as Wing, TrueMoney.

After 6 months, a qualitative assessment will be conducted to evaluate feasibility, acceptability and appropriateness of the intervention and to identify barriers and facilitators.

Several ART sites/HIV clinics particularly in charge of key populations will be specifically selected as participating centers in order to collect information on linkage to care or prevention services for positive and negative participants, respectively.

Tentative study agenda

- Protocol submission: December 2022
- Study implementation: February 2023 July 2023
- Data collection: August 2023 April 2025 (18 months)
- Duration of the study: 24 months

6 STUDY POPULATION

MSM and TGW who are residing in Phnom Penh at the time of enrollment and meet the eligible criteria below are the study population:

Version 1.1 du 18/04/2022

- To be aged from 18 years old (legal age in Cambodia)
- For MSM, to have at least one oral or anal intercourse with another man in the past 12 months
- For TGW, to be biologically a male at birth and self-identified as a woman or third gender and have at least one oral, anal or vaginal intercourse with another man in the past 12 months

7 STUDY ENDPOINTS

Primary endpoint

 HIV self-testing uptake defined as the number of HIV self-tests delivered / total number of coupons distributed

Secondary endpoints

- Proportion of HIVST result's recorded / total number of HIVST delivered
- Proportion of paper and electronic coupons delivered
- Number of HIV tests realized / number of HIV tests results non recorded
- Proportion of MSM/TGW with positive HIV self-tests linked to an ART site
- Proportion of negative MSM/TGW linked to PrEP services
- Characteristics of participants recruited (sociodemographic, sexual behavior, utilization of dating application, substance use) in comparison with IBBS 2019 report
- Proportion of participants with 6-monthly repeated HIV testing during 18 months

Outcomes of acceptability and appropriateness will be explored during focus groups: comfort, usefulness, suitability, confidentiality, credibility, advantages and barriers.

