1 STUDY SUMMARY

Clinicaltrial Id:

Title of Study: Pilot implementation of HIV self-testing delivery in private pharmacies combined to a Respondent Driven Sampling method to improve HIV testing for MSM and TGW in Phnom Penh

Short title - Sponsor N°: -ANRS 0100s

Sponsor: Institut national de la santé et de la recherche médicale - ANRS Emerging Infectious diseases (Inserm-ANRS| MIE)

Coordinating Investigator(s):

[name], University of Health Sciences, Cambodia

[name], SESSTIM, France

Participating countries: CAMBODIA AND FRANCE

Primary objective:

Evaluate the feasibility of HIV self-testing (HIVST) delivery by a private pharmacy network among men who have sex with men (MSM) and transgender women (TGW) recruited through a classic and digital Respondent Driven Sampling method to improve HIV testing in Phnom Penh, Cambodia

Secondary objectives:

- Evaluate the acceptability and appropriateness of the strategy
- Identify barriers and facilitators
- Estimate the linkage to confirmatory testing for those with a reactive test and linkage to HIV care and ART for those with a positive confirmatory HIV test
- Estimate linkage to pre-exposure prophylaxis (PrEP) services for negative participants
- Estimate the characteristics of participants and compare to those reported in Integrated Biological and Behavioral Survey (IBBS 2019) for MSM and TGW in Cambodia
- Evaluate the adherence of participants to a 6-monthly repeated HIV testing

Methodology:

An interventional pilot study using a mixed qualitative and quantitative approach will be carried out in order to evaluate the feasibility, acceptability and appropriateness of the strategy and to identify barriers and facilitators.

The participant recruitment method will be designed as a Respondent Driven Sampling (RDS) by recruiting initial seeds both at hotspots and on social networks. Prior to seed recruitment, a consultative meeting will be conducted in order to optimise the selection criteria of the seeds. The seeds will then distribute electronic and paper coupons to their networks physically and via social media, messaging and calling applications such as Twitter, Whatapp and Telegram (e-coupons).

Version 1.1 du 18/04/2022

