Each recruited participant will bring the coupon to be scanned at partner pharmacies to receive direct and free access to one HIVST kit. Partner pharmacies with a proper dedicated room/space securing privacy and secrecy in Phnom Penh are the study sites. There, trained community workers who get notified by partner at each visit of participant will do the study visit including information/consent (annexe 1 and 2), e-CRF filling (annexe 3) and give a link of an external website to send the HIV test results and receive information or advices. These recruited individuals will be considered as wave 1 of recruitment and will each receive 10 additional coupons to recruit the members of their networks. The next round of individuals recruited and enrolled will be considered as wave 2, and so on.

After 6 months, a qualitative assessment via focus groups will be conducted among MSM, TGW and pharmacists to evaluate feasibility, acceptability and appropriateness of the intervention and to identify barriers and facilitators.

Several ART sites/HIV clinics particularly in charge of key populations will be specifically selected as participating centers in order to collect information on linkage to care or prevention services for positive and negative participants, respectively.

Each participant will be followed during 18 months and encouraged to perform a 6-monthly HIV testing during this period.

Expected enrolment

A pragmatic approach is carried out in which the enrolment will be stopped at the end of the inclusion period or if the number of participants reaches a maximum of 1500.

Outcomes

With regard to the novel intervention, the outcomes will focus on its feasibility, adoption, acceptability and appropriateness.

The primary outcomes will be the HIV self-testing uptake defined as the number of HIV self-tests delivered / total number of coupons distributed

The secondary outcomes will be:

- Proportion of HIVST result's recorded / total number of HIVST delivered
- Proportion of paper and electronic coupons delivered and recorded
- Number of HIV tests realized / number of HIV tests results non recorded
- Proportion of MSM/TGW with positive HIV self-tests linked to an ART site
- Proportion of negative MSM/TGW linked to PrEP services
- Characteristics of participants recruited (sociodemographic, sexual behavior, utilization of dating application, substance use) in comparison with IBBS 2019 report

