14 STATISTICAL ANALYSES

Calculation of number of participants needed

We will use a pragmatic approach with the objective to recruit the maximum of MSM and TGW. According to the IBBS 2019, the estimated number of MSM in Phnom Penh is 6300 and the

Version 1.1 du 18/04/2022

estimated number of TGW is 1400.

With 1500 participants (1000 MSM and 500 TGW), we will be able to estimate an HIV self-test uptake of 70% to within a 95% confidence interval of +/- 2 – 2.5% (width of the confidence interval (in %) = $1.96 \times \sqrt{(p \times (1-p)/n)}$.

Analysis plan

Description of the characteristics at inclusion.

These variables will be described by their median, interquartile range, mean, standard deviation, or frequencies (%), as appropriate. These variables will be compared to those reported in the IBBS 2019 for MSM and TGW.

Primary outcome

The percentage, and its 95% confidence interval of HIV self-tests delivered among the total number of coupons distributed will be given and stratified by gender (MSM or TGW) and by type of coupons (paper or electronic).

Secondary outcomes

- The percentage and its 95% confidence interval of HIVST result's recorded among the total number of HIVST delivered will be given and stratified by gender (MSM or TGW)
- For those accepting to be contacted by phone, the percentage and its 95% confidence interval of HIVST realized among the number of HIV tests results non recorded will be given
- The percentage and its 95% confidence interval of participants with positive HIV selftests linked to an ART site will be given and stratified by gender (MSM or TGW)
- The percentage and its 95% confidence interval of participants with negative HIV selftests linked to PrEP services will be given and stratified by gender (MSM or TGW)
- The percentage and its 95% confidence interval of participants with 6-monthly repeated HIV testing during the 18 months (so 4 HIVSTs during the total duration of the study) will be given
- The probability of discontinuation of HIV testing and its 95% confidence interval, as well as the median time to the occurrence of HIV testing discontinuation, will be determined using a Kaplan Meier analysis, to take into account censored data due to lost of follow-up.

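### Primary endpoint is counted per coupon, but its only expected value and precision (70% ± 2–2.5 points) are computed on 1,500 participants, and coupons *distributed* is not defined

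*Protocol*

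**What the plan says.** The Study Summary and section 7 define the primary endpoint as "HIV self-testing uptake defined as the number of HIV self-tests delivered / total number of coupons distributed". Section 14 (Primary outcome) analyses the same ratio: the percentage of "HIV self-tests delivered among the total number of coupons distributed will be given and stratified by gender (MSM or TGW"), and also by paper or electronic coupon.

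The precision statement uses another unit. Section 14, like the Study Summary, says "With 1500 participants (1000 MSM and 500 TGW), we will be able to estimate an HIV self-test uptake of 70" per cent, to within 2 to 2.5 points, with the half-width formula 1.96 × √(p(1−p)/n).

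On how coupons move:
- Section 5: "Each recruited participant will bring the coupon to be scanned at partner pharmacies to receive direct and free access to one HIVST kit".
- Recruits "will each receive 10 additional coupons to recruit the members of their networks" (section 5). The 15 initial seeds also receive ten each, five electronic and five paper.
- Study Summary, on what seeds do next: "The seeds will then distribute electronic and paper coupons to their networks physically and via social media".
- Sections 5 and 8 give non-reactive participants further coupons for six-monthly retests over 18 months.

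A secondary endpoint also counts coupons. The Study Summary has "Proportion of paper and electronic coupons delivered and recorded" and section 7 has "Proportion of paper and electronic coupons delivered". Neither says at which step coupons are counted.

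**The concern.** Outside the seeds, a person becomes a participant by presenting a coupon and receiving a kit. The 1,500 participants are therefore, to a close approximation, the kits delivered at first visits. They cannot also be the denominator of kits over coupons. Counted per participant, first-kit uptake would be close to 100% by design.

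The denominator itself is open. *Distributed* could mean passed from a participant to a peer, or issued by the study to seeds and recruits. The same data could then give very different headline figures for the primary outcome. Section 7 also does not say whether retest coupons and kits count.

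Finally, the ratio is to be stratified by gender. The participant's characteristics are recorded at the pharmacy visit, after the scan, so an unredeemed coupon has no recipient gender and the stratum denominators cannot be formed as written.

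**Working it through.** **Inputs.** Expected uptake 0.70 and n = 1,500 (section 14); S = 15 seeds and 10 coupons per seed and per recruit (sections 5 and 9); one kit per recruit at entry (section 5); cap of 1,500 participants (Study Summary); four tests per person over the study with full adherence (section 14).

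**1. The stated precision.** 1.96 × √(0.7 × 0.3/1,500) = 2.32 points, inside the stated 2 to 2.5. Solving the formula for half-widths of 2.5 and 2 points gives n of about 1,291 and 2,017. The printed figure therefore uses 1,500 participants as denominator.

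**2. *Distributed* as handed on to peers.** With 1,500 kits at 70%:
- coupons = 1,500/0.70 = 2,143;
- half-width = 1.96 × √(0.21/2,143) = 1.94 points.

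That is 2,143/1,515 = 1.41 coupons handed on per person, out of ten received.

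**3. *Distributed* as issued.** With K recruits, each having one first-visit kit, coupons issued are 10(S + K), so

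ratio = K / (10(S + K)), which is below 10% for every K.

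| K | Coupons issued | Ratio |
|---|---|---|
| 50 | 650 | 7.7% |
| 300 | 3,150 | 9.5% |
| 1,500 | 15,150 | 9.9% |

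At K = 1,500 the half-width is 1.96 × √(0.099 × 0.901/15,150) = 0.48 points. If the seeds are inside the cap, 1,485/15,000 is also 9.9%. Reaching 70% would take 0.70 × 15,150 = 10,605 kits, about seven per recruit at the cap.

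The ratio depends only on S and K. Once redemption exceeds 10%, each recruiter brings in more than one recruit on average, chains grow until enrolment closes, and the ratio settles near 10% whatever the redemption. Coupons still outstanding at closure count as not taken up.

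**4. Retests, issued reading.** These are upper bounds, assuming every recruit completes three retests:
- retest kits and coupons both counted: 6,000/(15,150 + 4,500) = 30.5%;
- retest kits counted but not their coupons: 6,000/15,150 = 39.6%.

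**5. Clustering by recruiter.** The documents give no intracluster correlation (ICC). Assuming 0 to 0.30:
- handed on: design effect up to 1 + 0.41 × 0.30 = 1.12, half-width 1.94 to 2.06 points;
- issued: design effect up to 1 + 9 × 0.30 = 3.7, half-width 0.48 to 0.91 points.

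**The case against.** The protocol's own usage favours the first meaning. The Study Summary and sections 5 and 9 use the verb for passing coupons to peers. On that reading 70% is attainable and the corrected half-width, 1.94 points, is slightly better than the printed range. This stands. A reader might infer from the ten-coupon rule that 70% is impossible and that the endpoint is capped near 10%. The documents do not support that as a general statement, because it holds only if *distributed* means issued. Even so, the handed-on reading does not make 1,500 participants the right n.

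Nothing is sized on the 70%. Enrolment is described as pragmatic, 1,500 is a maximum, and no success threshold is set. This also stands, so the enrolment target is not undermined.

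Kits need not equal participants. Section 9 has the coupon scanned before eligibility and consent are checked, so some kits may go to people who do not enrol. That is a small correction and cannot turn the numerator into the denominator.

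Coupons might be withheld as the cap approaches, which would raise the issued ratio. The protocol does not say so.

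The count of coupons handed on may be in the e-CRF annexe or operating procedures, which are not shown. The point is therefore limited to the protocol text.

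A reader might also infer that a time-to-redemption analysis must become the primary measure. That does not follow: it would still count coupons never handed on as unredeemed. The choice can be left to the analysis plan.

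**Conclusion.** The inconsistency holds on either meaning: the endpoint and its analysis are per coupon, while the expected value and precision are per participant. The protocol itself fixes all three, so an analysis plan cannot reconcile them without the protocol being corrected.

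The size depends on the meaning chosen:
- **Handed on:** 70% ± 1.9 points on about 2,143 coupons before clustering, with no count of the step described in the text shown.
- **Issued:** at 1,500 first-visit kits, 9.9% ± 0.5 points before clustering. Here 70% is out of reach and the ratio says little about redemption.

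These figures assume one first-visit kit per recruit and, for the issued reading, ten coupons to every seed and recruit. The gender-stratified ratio cannot be computed as written on either reading. The consequence is a misstated precision and a primary result open to more than one value.

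**What to change.** 1. **Study Summary, sections 7 and 14:** define coupons distributed either as handed on to peers, stating how this is counted, or as issued to seeds and participants. Restrict numerator and denominator to first-visit recruitment coupons and kits, and report repeat tests separately.
2. **Study Summary (Statistical methods) and section 14:** replace the 70% on 1,500 participants with an expected value and precision computed on coupons for the chosen definition, noting that coupons are clustered by recruiter.
3. **If issued coupons are used:** state that the crude ratio is below 10% by design, and interpret uptake mainly from coupons issued long enough before enrolment closes. The window or time-to-redemption method can be set in the analysis plan.
4. **Section 14:** stratify the coupon-based ratio by the recruiter's gender, keeping coupon type as planned.

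The cost is mainly wording, possibly with ethics committee approval of the change. Paying 1 USD per recruited peer (section 9) already needs a link from coupon to recruiter. Recruits' issue dates can probably be taken from the pharmacy visit, but seeds' issue dates, or the handover to peers if that definition is chosen, may need minor extra logging. The stated uptake may also look less favourable.

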with the important details about the study. Once consent to the study, the seed is provided with two types of coupons for HIVST kit at partner pharmacy: 1- 5 electronic coupons (e-coupons) consisting of a pictured unique anonymous QR code and identifier and address of partner pharmacies 2- 5 paper coupons consisting of a printed unique anonymous QR code, identifier and address of partner pharmacies. The seeds will provide paper- and e-coupons to their networks physically and via social media, messaging and calling applications such as Twitter, Whatapp and Telegram (e-coupons). For online application and social media, a peer could be reached by chat or call.

When the participant arrives in a partner pharmacy, the coupon (unique QR code with identifier) will be scanned by the pharmacist prior to the free delivery of HIV self-test. Community workers (CWs) will be then alerted by the pharmacist for study visits to participant directly at the dedicated space at the pharmacy. During the visit with CW, participant will:

- Receive the information about the study
- Receive an ID
- Check for eligibility criteria
- Be requested for his/her consent to participate in the study and to different specific consents as receiving funds, being recontacted by phone and participation in FGD
- Fill in the detailed e-CRF for sociodemographic status, sexual behaviors, utilization of dating application, substance use, knowledge about PrEP and willingness to pay for HIV self-testing by using Tablet with the eventual assistance from a community worker
- Receive the information on HIV self-testing instructions, list of partner pharmacies, helpline phone number, location of the 2 partners ART sites, location of the HIV clinics with prevention services and PrEP delivery availability
- Be provided one free HIV self-testing kit delivered
- Receive the link of the external website to performance HIV test, interpret and send the HIV test result, receive necessary information and in case of non-reactive, to receive another coupon for 6-monthly test during 18 months
- Receive 10 (paper or electronic) coupons to distribute to peers
- Be asked if the participant would agree to be recontacted for an eventual participation in a focus group

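### The primary endpoint, kits delivered over coupons distributed, does not separate pharmacy delivery from coupon circulation among peers, so it cannot by itself answer the pharmacy-delivery part of the primary objective

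*Protocol*

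**What the plan says.** The primary objective (Protocol, section 4) has two parts. The first is to "Evaluate the feasibility of HIV self-testing (HIVST) delivery by a private pharmacy network". The second describes how the target population is reached: "recruited through a classic and digital Respondent Driven Sampling method to improve HIV testing in Phnom Penh, Cambodia". Section 3 (Study main hypothesis) ranks them. Pharmacies being able to deliver kits is the main hypothesis, and RDS reaching hidden networks is the second.

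The primary endpoint (sections 1, 7 and 14) is "HIV self-testing uptake defined as the number of HIV self-tests delivered / total number of coupons distributed".

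The coupon rules are in sections 5 and 9. On seeds, "15 initial seeds will be recruited", each with 5 electronic and 5 paper coupons. Those recruited "will each receive 10 additional coupons to recruit the members of their networks", and the same holds for later waves. Enrolment ends at 1500 participants or at the end of the inclusion period (section 1).

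At the pharmacy, the coupon "will be scanned by the pharmacist prior to the free delivery of HIV self-test" (section 9). The community worker is then alerted, and the visit covers eligibility, consent, the e-CRF and the kit. No listed endpoint uses scanned coupons or arriving people as its denominator.

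**The concern.** Delivery at the pharmacy starts at the scan and can fail afterwards: the person may leave before the community worker comes, decline consent, or be found ineligible. In the primary endpoint such a case has the same effect as an issued coupon that nobody ever brought in. Both add to the denominator and not to the numerator.

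The 10-coupon rule makes this worse. A person who is served adds one kit and ten coupons. A person who is not served adds neither. Poor service therefore slows both counts together, and the ratio tends to a value set by the coupon rule.

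Two misreadings are possible. A value near 10% could be taken as weak pharmacy delivery when it follows from issuing ten coupons per person. And a real loss of people between scan and kit could leave the primary result almost unchanged.

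**Working it through.** **The plan's own figure.** Section 14 gives a half-width of 2 to 2.5 points for 70% uptake with 1500 participants: 1.96 × √(0.70 × 0.30 / 1500) = 2.32 points. It reproduces. It treats uptake as a proportion of participants, whereas the endpoint is a proportion of coupons.

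**Inputs from the protocol.** 15 seeds, 10 coupons per seed, 10 coupons per enrolled recruit, at most 1500 participants.

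**Counting conditions.** Coupons are counted as issued, first kits only, everyone enrolled receives coupons (including the last wave), and no later seeds. With N recruits enrolled besides the seeds:

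ratio = N / [10 × (N + 15)]

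- N = 300: 300 / 3150 = 9.5%
- N = 1500: 1500 / 15150 = 9.9%

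Counting the seeds within N gives (N − 15) / (10N), and the same 9.5% and 9.9%.

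**Sensitivity to service, 1500 arrivals held fixed**

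| Share of arrivals served | Kits | Ratio |
|---|---|---|
| 100% | 1500 | 9.90% |
| 70% | 1050 | 9.86% |
| 50% | 750 | 9.80% |
| 20% | 300 | 9.52% |
| 10% | 150 | 9.09% |

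Turning away half of the arrivals moves the ratio by 0.1 point. A simple binomial half-width at 750 kits on 7650 coupons is 1.96 × √(0.098 × 0.902 / 7650) = 0.67 points.

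**Letting the chains run.** The ratio factorises as (coupons scanned / coupons issued) × (kits delivered / coupons scanned). A chain sustains itself only if 10 × (share of coupons reaching a pharmacy) × (share served) exceeds 1. Simulated chains, cap 1500; the reach values are assumptions, since the protocol gives none:

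| Coupons reaching a pharmacy | Mean ratio, 100% served | Mean ratio, 60% served | Median enrolment, 100% against 60% |
|---|---|---|---|
| 20 to 30% | 9.9% | 9.9% | 1500 against 1500 |
| 15% | 9.9% | 8.5% | 1500 against about 100 |
| 12% | 9.9% | 6.8% | 1500 against 35 |
| 8% | 7.5% | 4.6% | 50 against 13 |

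In every row, kits per scan is about 100% or 60%, which identifies the step.

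At the cap the factorisation shows what is hidden. With 60% served, 1500 kits need 1500 / 0.6 = 2500 scans, so scanned/issued is 2500 / 15150 = 16.5%, and 16.5% × 60% = 9.9%. With all served, it is 9.9% × 100% = 9.9%.

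**If repeat tests count.** Section 14 foresees 4 tests in 18 months, so up to 3 repeat coupons each, or 4500 more at 1500 enrolled. The ratio becomes 1500 / 19650 = 7.6% if none are used, 3750 / 19650 = 19.1% if half are, and 6000 / 19650 = 30.5% if all are. That movement reflects retesting, not service to arrivals.

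**The case against.** A reader might infer that the endpoint cannot answer the primary objective at all. The documents do not support that. The objective continues into RDS recruitment, and the study title presents pharmacy delivery combined with RDS. Kits per coupon is a measure of that whole chain. What stands is narrower: it does not isolate the pharmacy step.

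A reader might also infer that the value stays near 9.9% however well the pharmacies perform. That holds only under the conditions above. When reach times service falls below 10%, chains die out and both the ratio and enrolment drop visibly. The protocol does not limit the endpoint to first kits. Nor does it say whether a coupon counts as distributed when the study hands it out or when a peer passes it on; section 9 has participants receive coupons in order to distribute them. On the second reading, coupons never passed on leave the denominator and the formula no longer applies. These points limit the size of the effect. They also show that the endpoint's terms need defining. They do not remove the attribution problem, because the ratio remains a product of two steps.

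Sections 1 and 5 also assign feasibility to focus groups, and the pharmacist topics in section 9 include logistics and time. That is useful evidence, but it gives no delivery proportion. The protocol sets no threshold below which the strategy is declared infeasible, so a misreading of a low value is a risk, not a certainty.

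Finally, kits per scan would be a poor sole primary endpoint. Ten arrivals and ten kits would score 100% even if almost nobody came. It also reflects waiting for the community worker and consent, which are study procedures. That is a good reason not to replace the existing ratio.

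**Conclusion.** The point holds in a limited form. The primary endpoint addresses the combined RDS-plus-pharmacy strategy but cannot, on its own, answer the pharmacy-delivery part of the objective, which section 3 makes the main hypothesis.

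With issued coupons, first kits and self-sustaining chains, the 10-coupon rule holds it just under 10% and it barely registers how many arrivals are served. At 20 to 30% reach, a network serving 60% of arrivals is indistinguishable from one serving all. At about 15% reach or below, poor service does lower the ratio, but not in a way that can be told apart from coupons failing to circulate. The reach values are assumptions.

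This does not prevent the study from running. It is an inexpensive improvement that should be made before the primary result is interpreted.

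**What to change.** 1. Keep the existing ratio as the measure of the combined strategy. Restrict it to recruitment coupons and first kits, and define distributed as issued by the study.
2. Beside it, as a co-reported primary feasibility measure, add first kits delivered / recruitment coupons scanned at the pharmacy, among people not found ineligible. Record the reason for each non-delivery: left before the community worker came, refused consent, or not eligible. The reasons separate pharmacy problems from study procedures.
3. Report recruitment coupons scanned / issued, noting that coupons still unused when enrolment stops lower this figure.
4. State in sections 7 and 14 that the combined ratio, so defined, is bounded near 10% by the 10-coupon rule, so that a low value is not read as pharmacy failure.

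The cost is an amendment to the endpoint wording, one extra field tied to the existing QR scan, and scan logs kept by anonymous coupon number for people who do not consent. No additional participants or staff are needed.
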